#### **9.4.3. Secondary endpoint(s)**

Data for each of the secondary outcome measures will be statistically analyzed for within and between group changes via analysis of variance (ANOVA), *t*-tests, or chi-square tests as appropriate.

#### **9.4.4. Tertiary/exploratory endpoint(s)**

The Statistical Analysis Plan will describe any planned tertiary/exploratory analyses in greater detail.

#### **9.4.5. Other safety Analyses**

There will not be a formal statistical analysis for safety endpoints (adverse events, etc.); however, all adverse events will be summarized via tables and descriptive statistics as appropriate.

### **9.5. Interim Analyses**

Not Applicable, i.e., there is not a planned interim analysis for this study.

### **9.6. Data Monitoring Committee (DMC)**

Not Applicable, i.e., there is not a DMC for this study.

## 10. Supporting Documentation and Operational Considerations

### 10.1. Appendix 1: Regulatory, Ethical, and Study Oversight Considerations

#### 10.1.1. Regulatory and Ethical Considerations

- This study will be conducted in accordance with the protocol and with the following:
  - Consensus ethical principles derived from international guidelines including the Declaration of Helsinki and Council for International Organizations of Medical Sciences (CIOMS) International Ethical Guidelines
  - Applicable ICH Good Clinical Practice (GCP) Guidelines
  - Applicable laws and regulations
- The protocol, protocol amendments, ICF, Investigator Brochure, and other relevant documents (e.g., advertisements) must be submitted to an IRB/IEC by the investigator and reviewed and approved by the IRB/IEC before the study is initiated.
- Any amendments to the protocol will require IRB/IEC approval before implementation of changes made to the study design, except for changes necessary to eliminate an immediate hazard to study participants.
- The investigator will be responsible for the following:
  - Providing written summaries of the status of the study to the IRB/IEC annually or more frequently in accordance with the requirements, policies, and procedures established by the IRB/IEC
  - Notifying the IRB/IEC of SAEs or other significant safety findings as required by IRB/IEC procedures
  - Providing oversight of the conduct of the study at the site and adherence to requirements of 21 CFR, ICH guidelines, the IRB/IEC, European regulation 536/2014 for clinical studies (if applicable), and all other applicable local regulations

#### 10.1.2. Financial Disclosure

Investigators and sub-investigators will provide the sponsor with sufficient, accurate financial information as requested to allow the sponsor to submit complete and accurate financial certification or disclosure statements to the appropriate regulatory authorities. Investigators are responsible for providing information on financial interests during the course of the study.

**10.1.3. Informed Consent Process**

- The investigator or his/her representative will explain the nature of the study to the participant or his/her legally authorized representative and answer all questions regarding the study.
- Participants must be informed that their participation is voluntary. Participants will be required to sign a statement of informed consent that meets the requirements of 21 CFR 50, local regulations, ICH guidelines, Health Insurance Portability and Accountability Act (HIPAA) requirements, where applicable, and the IRB/IEC or study center.
- The medical record must include a statement that written informed consent was obtained before the participant was enrolled in the study and the date the written consent was obtained. The authorized person obtaining the informed consent must also sign the ICF.
- Participants must be re-consented to the most current version of the ICF(s) during their participation in the study.
- A copy of the ICF(s) must be provided to the participant or the participant's legally authorized representative.
- Participants who are rescreened are required to sign a new ICF.

**10.1.4. Data Protection**

- Participants will be assigned a unique identifier. Any participant records or datasets that are transferred outside of study site will contain the identifier only; participant names or any information which would make the participant identifiable will not be transferred.
- The participant must be informed that his/her personal study-related data will be used by the study team in accordance with local data protection law. The level of disclosure must also be explained to the participant who will be required to give consent for their data to be used as described in the informed consent
- The participant must be informed that his/her medical records may be examined by Clinical Quality Assurance auditors or other authorized personnel appointed by the sponsor, by appropriate IRB/IEC members, and by inspectors from regulatory authorities.

**10.1.5. Clinical Monitoring**

Clinical site monitoring is conducted to ensure that the rights and well-being of trial participants are protected, the reported trial data are accurate, complete, and verifiable, and the conduct of the trial is in compliance with the currently approved protocol/amendment(s), with International Conference on Harmonization cGCP), and with applicable regulatory requirement(s).

This document, including any source code, is the property of [Clinvest Research LLC](#), and may contain proprietary, confidential, or legally privileged information. No part of this report, or any information contained therein, may be disseminated without the written consent of [Clinvest Research LLC](#).

- Monitoring for this study will be performed by the Contract Research Organization (CRO).
- Details of clinical site monitoring are documented in a Monitoring Plan (MP). The MP describes in detail who will conduct the monitoring, at what frequency monitoring will be done, at what level of detail monitoring will be performed, and the distribution of monitoring reports.

#### **10.1.6. Data Quality Assurance**

- All participant data relating to the study will be recorded on printed or electronic CRF unless transmitted to the sponsor or designee electronically (e.g., laboratory data). The investigator is responsible for verifying that data entries are accurate and correct by physically or electronically signing the CRF.
- The investigator must maintain accurate documentation (source data) that supports the information entered in the CRF.
- The investigator must permit study-related monitoring, audits, IRB/IEC review, and regulatory agency inspections and provide direct access to source data documents.
- Monitoring details describing strategy (e.g., risk-based initiatives in operations and quality such as Risk Management and Mitigation Strategies and Analytical Risk-Based Monitoring), methods, responsibilities and requirements, including handling of noncompliance issues and monitoring techniques (central, remote, or on-site monitoring) are provided in the Monitoring Plan.
- The sponsor or designee is responsible for the data management of this study including quality checking of the data.
- The sponsor assumes accountability for actions delegated to other individuals (e.g., Contract Research Organizations).
- Study monitors will perform ongoing source data verification to confirm that data entered into the CRF by authorized site personnel are accurate, complete, and verifiable from source documents; that the safety and rights of participants are being protected; and that the study is being conducted in accordance with the currently approved protocol and any other study agreements, ICH GCP, and all applicable regulatory requirements.
- Records and documents, including signed ICFs, pertaining to the conduct of this study must be retained by the investigator for 2 years after study completion unless local regulations or institutional policies require a longer retention period. No records may be destroyed during the retention period without the written approval of the sponsor. No

records may be transferred to another location or party without written notification to the sponsor.

#### **10.1.7. Source Documents**

- Source documents provide evidence for the existence of the participant and substantiate the integrity of the data collected. Source documents are filed at the investigator's site.
- Data reported on the CRF or entered in the eCRF that are transcribed from source documents must be consistent with the source documents or the discrepancies must be explained. The investigator may need to request previous medical records or transfer records, depending on the study. Also, current medical records must be available.
- Data for this trial will be primarily collected in a web-based electronic data capture (EDC) REDCap platform. The EDC access will be supplied by the sponsor with relevant training support to sites. Sites will be responsible for training study subjects in the EDC system. All data specified should be captured by the site personnel or participants in the EDC system. When possible, all eCRFs are to be completely filled out by personnel administering the study procedures in real-time at the time of the visit. All eCRFs that are completed in real-time at the time of the visit will be considered source documentation for this study. When allowed by the site's IRB, any data entered on an eCRF which was not entered into REDCap in real-time at the time of the visit, or where such data originated from an external paper source document (e.g., signed Informed Consent Form (ICF) signature page, laboratory, procedure findings, etc.), will require paper source documents to be uploaded into the REDCap system to allow for source data verification monitoring. When a site's IRB does not allow for specific paper source documents to be uploaded into REDCap (e.g., the ICF signature pages, etc.), then those paper source documents will be reviewed during on-site monitor visits.
- It is the investigator's responsibility for the collection and reporting of all clinical, safety, and laboratory data entered on the CRF and confirmation the data is accurate, authentic, attributable, complete, and consistent. The investigator or sub-investigator must sign the CRFs within the EDC system to attest the information contained with the CRF is true and causality of any safety information has been assessed. All data must be reviewed and signed by the investigator or sub-investigator at the conclusion of the study for each subject. The CRFs should not be made available in any form to third parties, without written permission from the sponsor.

#### **10.1.8. Study and Site Start and Closure**

The study start date is the date on which the clinical study will be open for recruitment of participants. The first act of recruitment is the first site open and will be the study start date.

The sponsor designee reserves the right to close the study site or terminate the study at any time for any reason at the sole discretion of the sponsor. Study sites will be closed upon study completion. A study site is considered closed when all required documents and study supplies have been collected and a study-site closure visit has been performed.

The investigator may initiate study-site closure at any time, provided there is reasonable cause and sufficient notice is given in advance of the intended termination.

Reasons for the early closure of a study site by the sponsor or investigator may include but are not limited to:

- Failure of the investigator to comply with the protocol, the requirements of the IRB/IEC or local health authorities, the sponsor's procedures, or GCP guidelines
- Inadequate recruitment of participants by the investigator
- Discontinuation of further study intervention development

If the study is prematurely terminated or suspended, the sponsor shall promptly inform the Investigators, the IECs/IRBs, the regulatory authorities, and any contract research organization(s) used in the study of the reason for termination or suspension, as specified by the applicable regulatory requirements. The Investigator shall promptly inform the participant and should assure appropriate participant therapy and/or follow-up

#### **10.1.9. Publication Policy**

- The results of this study may be published or presented at scientific meetings. If this is foreseen, the investigator agrees to submit all manuscripts or abstracts to Teva (financial sponsor) before submission. This allows the financial sponsor to protect proprietary information and to provide comments.
- Teva (financial sponsor) will comply with the requirements for publication of study results. In accordance with standard editorial and ethical practice, the financial sponsor will generally support publication of multicenter studies only in their entirety and not as individual site data. In this case, a coordinating investigator will be designated by mutual agreement.
- Authorship will be determined by mutual agreement and in line with International Committee of Medical Journal Editors authorship requirements.

This document, including any source code, is the property of [Clinvest Research LLC](#), and may contain proprietary, confidential, or legally privileged information. No part of this report, or any information contained therein, may be disseminated without the written consent of [Clinvest Research LLC](#).

## 10.2. Appendix 2: Clinical Laboratory Tests

- The tests detailed in Table 1 will be performed by the local laboratory.
- Protocol-specific requirements for inclusion or exclusion of participants are detailed in Section 5 of the protocol.
- Additional tests may be performed at any time during the study as determined necessary by the investigator or required by local regulations.
- Urine Pregnancy Testing

**Table 1: Protocol-Required Safety Laboratory Assessments**

Laboratory Assessments	Parameters			
Hematology	Platelet Count	RBC Indices: MCV MCH %Reticulocytes	White blood cell (WBC) count with Differential: Neutrophils Lymphocytes Monocytes Eosinophils Basophils	
	Red blood cell (RBC) Count			
	Hemoglobin			
	Hematocrit			
Clinical Chemistry 	Blood urea nitrogen (BUN)	Potassium	Aspartate Aminotransferase (AST)/ Serum Glutamic-Oxaloacetic Transaminase (SGOT)	Total and direct bilirubin
	Creatinine	Sodium	Alanine Aminotransferase (ALT)/ Serum Glutamic-Pyruvic Transaminase (SGPT)	Total Protein
	Glucose (nonfasting)	Calcium	Alkaline phosphatase	
Other Screening Tests	The results of each test must be entered into the CRF.			

Investigators must document their review of each laboratory safety report.

This document, including any source code, is the property of [Clinvest Research LLC](#), and may contain proprietary, confidential, or legally privileged information. No part of this report, or any information contained therein, may be disseminated without the written consent of [Clinvest Research LLC](#).

## 10.3. Appendix 3: Adverse Events: Definitions and Procedures for Recording, Evaluating, Follow-up, and Reporting

### 10.3.1. Definition of AE

#### AE Definition

- An AE is any untoward medical occurrence in a patient or clinical study participant, temporally associated with the use of study intervention, whether or not considered related to the study intervention.
- NOTE: An AE can therefore be any unfavorable and unintended sign (including an abnormal laboratory finding), symptom, or disease (new or exacerbated) temporally associated with the use of study intervention.

#### Events Meeting the AE Definition

- Any abnormal laboratory test results (hematology, clinical chemistry, or urinalysis) or other safety assessments (e.g., ECG, radiological scans, vital signs measurements), including those that worsen from baseline, considered clinically significant in the medical and scientific judgment of the investigator (i.e., not related to progression of underlying disease).
- Exacerbation of a chronic or intermittent pre-existing condition including either an increase in frequency and/or intensity of the condition.
- New conditions detected or diagnosed after study intervention administration even though it may have been present before the start of the study.
- Signs, symptoms, or the clinical sequelae of a suspected drug-drug interaction.
- Signs, symptoms, or the clinical sequelae of a suspected overdose of either study intervention or a concomitant medication. Overdose per se will not be reported as an AE/SAE unless it is an intentional overdose taken with possible suicidal/self-harming intent. Such overdoses should be reported regardless of sequelae.
- The signs, symptoms, and/or clinical sequelae resulting from lack of efficacy will be reported as AE or SAE if they fulfil the definition of an AE or SAE. Also, “lack of efficacy” or “failure of expected pharmacological action” also constitutes an AE or SAE.

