### 9.2. Sample Size Determination

To determine the needed sample size for this study we utilized G\*Power Version 3.1.9.3 to conduct a power analysis for the Primary Endpoint analysis (repeated measures ANOVA, within-between interaction) comparing baseline MIBS-4 scores to treatment month(s) MIBS-4 scores between 50% responders and non-responders. Based on prior research, we expect an approximate equal proportion of responders and non-responders in this open-label study. The power analysis indicated that a total of 36 subjects would be adequate to detect a medium effect ( $f= 0.25$ ), with alpha set at 0.05, and a power of .95. To account for a 10% early withdrawal rate, a total of 40 subjects should be enrolled in the study.

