**Events NOT Meeting the AE Definition**

- Any clinically significant abnormal laboratory findings or other abnormal safety assessments which are associated with the underlying disease, unless judged by the investigator to be more severe than expected for the participant's condition.
- The disease/disorder being studied or expected progression, signs, or symptoms of the disease/disorder being studied, unless more severe than expected for the participant's condition.
- Medical or surgical procedure (e.g., endoscopy, appendectomy): the condition that leads to the procedure is the AE.
- Situations in which an untoward medical occurrence did not occur (social and/or convenience admission to a hospital).
- Anticipated day-to-day fluctuations of pre-existing disease(s) or condition(s) present or detected at the start of the study that do not worsen.

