**10.3.2. Definition of SAE**

If an event is not an AE per definition above, then it cannot be an SAE even if serious conditions are met (e.g., hospitalization for signs/symptoms of the disease under study, death due to progression of disease).

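### Does counting lack of efficacy as an adverse event distort the safety summary?

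*Combined protocol and SAP*

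**What the plan says.** The last bullet under Events Meeting the AE Definition (Section 10.3.1) has two sentences. The first deals with the clinical consequences of treatment failure, which count conditionally: those "resulting from lack of efficacy will be reported as AE or SAE if they fulfil the definition of an AE or SAE". The second deals with treatment failure itself and carries no condition: "Also, “lack of efficacy” or “failure of expected pharmacological action” also constitutes an AE or SAE". An earlier bullet in the same list makes worsening of an existing condition reportable: "Exacerbation of a chronic or intermittent pre-existing condition including either an increase in frequency and/or intensity of the condition".

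The companion list, Events NOT Meeting the AE Definition, removes the disease under study and its "expected progression, signs, or symptoms of the disease/disorder being studied, unless more severe than expected". It also removes ordinary day-to-day variation in conditions "present or detected at the start of the study that do not worsen". Section 10.3.2 adds: "If an event is not an AE per definition above, then it cannot be an SAE even if serious conditions are met".

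Two statistical sections bear on the point. Section 9.2 says "we expect an approximate equal proportion of responders and non-responders in this open-label study". Section 9.4.5 rules out formal testing of safety endpoints and says "all adverse events will be summarized via tables and descriptive statistics as appropriate". Section 9.4 leaves further detail to an SAP that is to be finalised before database lock and takes precedence over the protocol. The combined document contains no separate SAP text.

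**The concern.** Take a participant whose migraine simply carries on as before. The exclusion list suggests that nothing is to be reported. The unconditional sentence suggests that the failure of the drug is itself an event. With no definition to decide between them, sites in a multicenter study could answer differently.

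The case would not be rare, because the study is built around comparing responders with non-responders and expects them in about equal numbers. Safety and tolerability is secondary endpoint 7 and rests largely on adverse events. There is no control arm in which the same reporting habit would show up. If many non-responders were given a lack-of-efficacy entry, the proportion with at least one adverse event would be part harm, part non-response and part site custom. Each entry would also need an intensity grade, a causality assessment and follow-up. Because the sentence mentions SAEs as well as AEs, 24-hour reporting could be drawn in.

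**Working it through.** **Base figures.** The plan's sample size reproduces. For the within-between interaction in a repeated measures ANOVA, take 2 groups, 4 visits (Visits 2 to 5), f = 0.25 and alpha = 0.05. Assume a correlation of 0.5 between visits and sphericity, neither of which is stated. The noncentrality is 0.25² × 36 × 4 / (1 − 0.5) = 18, with 3 and (36 − 2) × 3 = 102 degrees of freedom. Power is 0.952, and 36 is the smallest even total that reaches 0.95. Allowing for 10% withdrawal, 36 / 0.90 = 40. An equal split gives 0.5 × 40 = 20 non-responders.

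**Possible effect on an any-AE proportion.** Let b be the proportion of participants with some other adverse event, and p the share of non-responders given a lack-of-efficacy entry. Neither is in the documents, so both are assumptions, as is independence between them. Then

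any-AE proportion = b + (1 − b) × 0.5 × p.

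| b | p = 10% | p = 25% | p = 50% | p = 100% |
|---|---|---|---|---|
| 20% | 24% | 30% | 40% | 60% |
| 40% | 43% | 47.5% | 55% | 70% |
| 60% | 62% | 65% | 70% | 80% |

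The number of participants added is 40 × (1 − b) × 0.5 × p = 20p(1 − b). At p = 10% that is 1.6, 1.2 or 0.8 participants for b = 20%, 40% or 60%. The large figures need p near 100%.

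**Does the text push p upwards?** No section says that a participant who is not a 50% responder thereby shows lack of efficacy; such a person may have partial benefit. Section 9.2 uses the equal split only for sample size. Under Section 8.3 adverse events are reported by the participant, with the investigator responsible for detecting and recording them. Section 8.3.2 prefers open, non-leading questions. Section 4.1 has sites review the diary for compliance, and nothing tells them to work out responder status. These points make blanket entry unlikely, though they do not fix p.

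**Do the rules contradict each other?**

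- Worsening migraine is reportable under both lists: as an exacerbation in one, and through the more-severe-than-expected exception in the other.
- Unchanged symptoms fall under the exclusions.
- A judgement that the drug has failed is what the unconditional sentence addresses. The exclusion list does not mention it.
- Section 10.3.2 only makes AE status a precondition for SAE status. The seriousness criteria listed there must still be met.

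The two sentences of the bullet therefore have different objects. What is missing is a definition.

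**Can the analyst deal with it?** Section 9.4.5 names no overall any-AE proportion and neither requires nor forbids a separate row. Section 10.3.3 has every event recorded in the CRF. If entries recorded only as lack of efficacy can be recognised there, a count without them returns b whatever p was and however sites differed. Showing the summary both with and without them uses data already collected.

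**The case for a change.** The best argument for a change is that the word introducing the second sentence signals an extra category, so it cannot be read as a restatement. Investigators are left to apply an undefined term in a study where non-response is expected in about half the participants. A table row can separate entries after the fact, but it cannot make sites report alike. The SAP is still to come and a clarifying sentence would cost little.

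Part of this stands. The term is undefined, sites could differ, and a site that records unchanged migraine under another label would be harder to separate out. Follow-up, causality assessment and possibly SAE reporting are touched as well as the summary table.

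The inference from half non-responders to an inflated safety summary does not stand. It needs a link between responder class and adverse event that the protocol does not make, and the striking percentages come wholly from assumed values of p and b. Fixing in advance an overall incidence that leaves these entries out would bring its own difficulty. Section 9.4.5 covers all adverse events, so if the sponsor keeps lack of efficacy as an event, that figure would omit events the protocol defines as such.

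**Conclusion.** No change to the plan is needed. This is an undefined reporting term, and the analyst can handle its effect on the tables within the existing wording by showing results with and without entries recorded only as lack of efficacy. The effect lies in an untested, single-arm safety description and in the handling of individual reports. The efficacy analyses and the sample size of 40 are unaffected.

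The size cannot be fixed from the documents. For background rates of 20% to 60%, it runs from 2 to 4 percentage points if a tenth of non-responders receive such an entry, up to 20 to 40 points if every one does. Nothing in the text supports the upper end. The conclusion assumes that such entries are recognisable in the CRF and that non-response is not automatically recorded as an event. Which reporting rule should apply to unchanged migraine is for the sponsor to settle; the documents do not decide it.
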